9.7.1 Main analysis

Baseline demographic and clinical characteristics

Descriptive summary will be presented for baseline demographic and clinical characteristics of all patients enrolled in Cohort A, Cohort B Pradaxa® initiators, and Cohort B VKA initiators, respectively. For continuous variables, number of patients, mean, standard deviation (SD), median, Q1 (lower quartile), Q3 (upper quartile), minimum, and maximum will be presented. For categorical variables, frequency and percentage will be presented for each category.

Primary outcomes

For Cohort A, descriptive summary will be presented for PACT-Q2 score at baseline visit (Visit 1), Visit 2, and Visit 3 using measure of central tendency and variation (mean \pm SD, or median with inter-quartile range (IQR)). The PACT-Q2 score at Visit 2 and Visit 3 will be compared with the PACT-Q2 score at baseline visit, respectively, using paired t-test or Wilcoxon signed-rank test based on the distribution of the data.

For Cohort B, the patients newly initiated Pradaxa® or VKA will be matched with a ratio of 1:1 based on the propensity score. The covariates age, gender, body weight, CHA₂DS₂-VASC score, HAS-BLED score, kidney function (creatinine clearance), stroke and/or bleeding related risk factors, co-morbidities, and/or concomitant therapies, **if available**, will be included in the propensity score model. Details of the propensity score model and the matching procedure, such as the choice of algorithm and caliper width will be specified in the SAP. Descriptive summary of the baseline characteristics will be presented for and compared between the matched patients to check the balance of baseline characteristics between the two groups of Cohort B after propensity score matching. Moreover, standardized difference will be calculated as a measure of the balance of baseline characteristics after propensity score matching. Analyses of PACT-Q2 score will be performed on propensity score matched Pradaxa® initiators and VKA initiators. Descriptive summary will be presented for PACT-Q2 score at Visit 2 and Visit 3 using mean \pm SD, or median with IQR. PACT-Q2 score will be compared between matched Pradaxa® initiators and VKA initiators using paired t-test or Wilcoxon signed-rank test.

Secondary outcomes

For Cohort A, the PACT-Q2 score at Visit 2 and Visit 3 will be compared using paired t-test or Wilcoxon signed-rank test based on the distribution of the data.

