## 7.4 Sample Size

It is planned that approximately 1000 patients from around 20 medical centers or regional hospitals will be recruited in the study. An estimated sub-group allocation basing on real-world practice in Taiwan includes approximately 300 patients in Cohort A (patients switched from VKA to Pradaxa®) and around 700 patients in Cohort B (patients newly initiated Pradaxa® or VKA), with about 500 patients receiving Pradaxa® and 200 patients receiving VKA. Consecutive enrolment will be performed during whole recruitment period to minimize selection bias. The actual number of patients in each cohort will be according to the patient distribution in the real-world practice.

Total number		1000	
Estimated number in sub-grouping	Cohort A —VKA switches to Pradaxa®		300
	Cohort B —Newly initiator	Pradaxa®	500
		VKA	200

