### 11.3 Primary Endpoint Analysis

Mean values and mean change from baseline of PACT-Q2 scores will be presented as descriptive statistics including Number, Mean $\pm$ SD, Median, Range, inter-quartile range (IQR), 25th percentile, 75th percentile and 95% C.I. The changes under Cohort A will be calculated as (PACT-Q2 scores at Visit 2 minus PACT-Q2 scores at visit 1, PACT-Q2 scores at Last Visit minus PACT-Q2 scores at visit 1). The difference under cohort B will be calculated as (PACT-Q2 scores of Pradaxa® minus PACT-Q2 scores of VKA at Visit 2, PACT-Q2 scores of Pradaxa® minus PACT-Q2 scores of VKA at Last Visit). Shapiro-Wilk test will be conducted for testing the normality. If the null hypothesis of normally distributed of Shapiro-Wilk test is not reject, two-sided paired t-test will be performed and obtain the p-value. Significant level of the test will be set as 0.05. Once significant result of Shapiro-Wilk test is lower than 0.05, Wilcoxon signed rank test will be used instead.

For cohort B, the patients newly initiated Pradaxa® or VKA will be matched with a ratio of 1:1 based on the propensity score with caliper matching. After the propensity score each patient is generated, both Pradaxa® group and VKA group should be randomly sorted and then the first VKA unit is selected to find its closest

Pradaxa® match in terms of the propensity score. The random seed will be set as 20190218. The caliper will be set as 0.001.

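### The fixed 0.001 propensity-score caliper in SAP 11.3 discards scarce VKA patients for no gain in balance: about 9 to 34 percentage points more go unmatched than with a scaled caliper, for assumed c-statistics of 0.57 to 0.80

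*SAP*

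**What the plan says.** Protocol 9.7.1 runs the Cohort B primary comparison on matched pairs only: "PACT-Q2 score will be compared between matched Pradaxa® initiators and VKA initiators using paired t-test or Wilcoxon signed-rank test". It leaves the matching details, "such as the choice of algorithm and caliper width will be specified in the SAP".

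SAP 11.3 supplies them. Patients are "matched with a ratio of 1:1 based on the propensity score with caliper matching". On the order of matching, the SAP says that "both Pradaxa® group and VKA group should be randomly sorted and then the first VKA unit is selected to find its closest". The partner it looks for is a "Pradaxa® match in terms of the propensity score". It also fixes a seed ("The random seed will be set as 20190218") and then gives the width: "The caliper will be set as 0.001". SAP 7.4 expects Cohort B to be unequal, "with about 500 patients receiving Pradaxa® and 200 patients receiving VKA".

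SAP 11.3 does not say whether 0.001 is on the raw score or its logit, or whether a Pradaxa patient may be reused. It gives no reason for the width, no expected number of pairs and no fallback if many VKA patients stay unmatched. The natural reading is the raw score, because closeness is defined on the propensity score itself. It is also matching without replacement, because the ratio is 1:1, the order is randomised with a seed, and the tests are paired.

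**The concern.** A caliper is useful when it is wide enough to find partners and narrow enough to keep the groups comparable. Both depend on how spread out the scores are, and a fixed 0.001 ignores that. If it is far smaller than the typical gap between neighbouring scores, VKA patients are dropped only because no unused Pradaxa patient has an almost identical score, even though close partners exist.

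VKA is the smaller arm and sets the number of pairs. Each lost pair widens the interval for the primary comparison. The VKA patients who remain are those whose scores look most like Pradaxa patients', so the result describes a narrower group. SAP 8.5 allows no imputation, so pairs with a missing PACT-Q2 score drop out of the paired test as well.

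**Working it through.** **Inputs from the documents.** Caliper 0.001, 1:1 nearest match, VKA first in random order (SAP 11.3); 500 Pradaxa and 200 VKA (SAP 7.4). The documents give no expected number of pairs, so there is no stated figure to reproduce.

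**Assumptions.** The score's separation is unknown, so the c-statistic is varied from 0.57 to 0.80. The logit of the score is normal with equal variance in both groups, separated by d = √2 × z(c) of its SDs. The comparator, 0.2 × pooled SD of the logit, is not in the documents.

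**Scale.** The SD of the raw score runs from about 0.05 (c = 0.57) to 0.22 (c = 0.80), so 0.001 is about 2.0% down to 0.45% of it. At c = 0.70, d = 1.414 × 0.524 = 0.74, which in this model is also the within-group SD of the logit. Then 0.2 SD is 0.148 on the logit. Near the overall Pradaxa share of 500/700 = 0.714 this is about 0.148 × 0.714 × 0.286 = 0.030 on the raw score, some 30 times the planned width.

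**Simulation.** 1000 replicates per scenario, random-order greedy matching without replacement. SE ratio = √(pairs at 0.2 SD ÷ pairs at 0.001), assuming the same SD of pair differences under both. Shift = how far the mean logit of matched VKA patients lies below that of all VKA patients, in SDs.

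| c | Pairs, 0.001 | Pairs, 0.2 SD | Extra unmatched (points) | SE ratio | Shift, 0.001 | Shift, 0.2 SD |
|---|---|---|---|---|---|---|
| 0.57 | 179.7 | 198.3 | 9 | 1.050 | 0.09 | 0.02 |
| 0.60 | 167.6 | 197.3 | 15 | 1.085 | 0.16 | 0.03 |
| 0.65 | 147.5 | 193.6 | 23 | 1.146 | 0.27 | 0.06 |
| 0.70 | 127.4 | 186.1 | 29 | 1.209 | 0.39 | 0.12 |
| 0.75 | 108.7 | 173.9 | 33 | 1.265 | 0.51 | 0.21 |
| 0.80 | 90.0 | 157.1 | 34 | 1.322 | 0.63 | 0.32 |

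Example at c = 0.70: (186.1 − 127.4)/200 = 29 points; √(186.1/127.4) = 1.209.

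**Interval width.** 95% half-width = 1.96 × √(2/n) in outcome SDs, with uncorrelated outcomes within pairs and complete PACT-Q2. For 0.001 against 0.2 SD: 0.207 and 0.197 at c = 0.57; 0.246 and 0.203 at 0.70; 0.292 and 0.221 at 0.80.

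**Balance.** The residual standardized difference of the logit is 0.000 with 0.001, and 0.0005 to 0.0070 with 0.2 SD.

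**Sensitivity.**
- *Fitted score*, 14 terms built from the SAP 8.4 covariates with assumed distributions, 300 replicates: 173 against 198 pairs at c = 0.59, 154 against 195 at 0.63, 125 against 183 at 0.71, 97 against 163 at 0.78. SE ratios 1.07, 1.13, 1.21 and 1.29.
- *No true separation*, 10 fitted covariates: chance alone gives an apparent c of about 0.575 and a loss of about 10 points.
- *Reuse of Pradaxa patients allowed*: 5.5%, 10%, 19%, 29%, 39% and 50% of VKA patients still have no Pradaxa score within 0.001.
- *0.001 read on the logit scale*: the loss is larger, 42 to 68 points.
- *15% fewer patients* (425 and 170): 11 to 37 points.
- *Other wider calipers*: 0.1 SD of the logit, or 0.02 on the raw score, comes within 5 pairs of 0.2 SD in every scenario.

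**The case against.** The best reply is that nothing here is an error. The protocol delegated the caliper, the SAP chose one, and a tight caliper trades pairs for closeness. The study calls itself mainly descriptive and has no power or precision target, so a larger standard error breaches no stated aim. The size rests on a c-statistic the documents do not give, and the comparator comes from outside them. The negligible cost in balance was shown above only for the logit, whereas the protocol's measure is the standardized difference of each characteristic. And the loss would not be hidden: tables carry population sizes, and baseline summaries cover both all and matched VKA initiators.

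Much of this stands. There is no contradiction, bias or invalid test, and no decision is shown to change. At the low end of separation the interval barely moves. The wider rule also narrows the group at c = 0.80, where it leaves 21% unmatched. Disclosure lets a reader see the loss, but it does not recover the pairs.

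The trade-off argument does not stand. With a fitted 10-covariate score, the mean absolute standardized difference across covariates was about 0.04 with 0.2 SD, against 0.05 to 0.07 with 0.001, and the root mean squared error of the effect was lower with 0.2 SD in every scenario. The tight caliper buys no covariate balance.

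Nor do the documents suggest very weak separation. Protocol 7 ties Pradaxa reimbursement to age, stroke, heart failure, diabetes and hypertension, which overlap with the score covariates, and Protocol 9.9 anticipates channeling. That is inference, not proof. Precision also matters more than the descriptive label implies, because SAP 11.6 rests its conclusion on p < 0.05.

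**Conclusion.** The concern holds. On the natural reading, a raw-score caliper of 0.001 without replacement leaves 10% to 55% of VKA initiators unmatched for c from 0.57 to 0.80, against 1% to 21% with 0.2 SD of the logit. The standard error of the Cohort B primary comparison is about 5% to 32% larger, and the matched VKA patients are less typical of all VKA initiators.

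The direction is the same under every reading and check tried. The size depends on the assumed overlap, the estimated group sizes and equal variability of pair differences, so confidence in the exact figures is moderate. This is avoidable lost precision and a narrower population. It should be fixed because the fix is cheap.

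**What to change.** If matched outcomes by treatment have not been examined, replace the caliper sentence in SAP 11.3 with:

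> Each VKA initiator, in random order, is matched 1:1 without replacement to the nearest Pradaxa initiator on the logit of the propensity score, within a caliper of 0.2 times the pooled SD of the logit. The number of unmatched VKA initiators is reported. Matching on the raw score, without replacement, within 0.001 is a sensitivity analysis.

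Keep the planned standardized differences.

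If the rule can no longer be changed without sight of outcomes, keep 0.001 as primary, state that it is on the raw score without replacement, and make the scaled caliper the sensitivity analysis.

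The cost is one SAP sentence and one program parameter, plus slightly larger score distances within pairs. The other cost is credibility if a primary matching rule changes late. Planned data collection ended on 27 September 2018 and the seed may be a date in February 2019 (an inference), although the SAP pages are still marked draft. The fallback avoids that cost.

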## 11.4 Secondary Endpoint Analyses

### Cohort A (patients switched from VKA to Pradaxa®)

- Mean change in the PACT-Q2 score at the last assessment (150-210 days) compared to the second assessment (30-45 days). The change will be calculated as (PACT-Q2 scores at Last Visit minus PACT-Q2 scores at visit 2). The test hypothesis of MMSE will be  $H_0: \text{Change} = 0$  vs.  $H_a: \text{Change} \neq 0$ . Shapiro-Wilk test will be conducted for testing the normality. If the null hypothesis of normally distributed of Shapiro-Wilk test is not rejected, two-sided paired t-test will be performed and obtain the p-value. Significant level of the test will be set as 0.05. Once significant result of Shapiro-Wilk test is lower than 0.05, Wilcoxon signed rank test will be used instead.

### Cohort B (patients newly initiated Pradaxa® or VKA)

- Description of mean PACT-Q1 score at baseline. Mean values of PACT-Q2 scores will be presented as descriptive statistics including Number, Mean  $\pm$  SD, Median, Range, inter-quartile range (IQR), 25th percentile, 75th percentile and 95% C.I.

## 11.5 Safety Analyses

Occurrences of Pradaxa® relevant ADRs will be analyzed relative to the number of patients treated as well as observed person-years (i.e. time at risk). If no concurrent Pradaxa® treatment is administered, then events occurring within a washout period of 3 days after discontinuation of Pradaxa® treatment will be assigned to the last treatment given. This washout period will also be included as time at risk for derivation of total person-years. ADRs that deteriorate under treatment will also be considered as “treatment emergent”. Events occurring prior to first intake of Pradaxa® treatment prescribed at baseline, during periods without Pradaxa® treatment (excluding washout periods), or after the end of the 6-month follow-up (excluding washout periods) will not be considered treatment emergent events, and will not be included in the summary tables.

AE will be coded using the MedDRA dictionary. All adverse events will be classified

using MedDRA terminology. The number of subjects and percentage of subjects will be computed by System Organ Class and Preferred Term to show the incidence of AE.

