9.7.3 Safety analysis

Safety analyses will be performed separately for Cohort A and Cohort B, and will include all enrolled patients with an actual follow-up. Statistical analysis and reporting of AEs (i.e. Pradaxa® relevant ADR (serious and non-serious), fatal AEs, and pregnancies) will be descriptive in nature and based on BI standards. No hypothesis testing is planned. The assessment of safety will be based mainly on the frequency of adverse events, which includes

all serious adverse events. All adverse events will be summarized with the coding term, severity, and relationship to study drug by frequency tables with the counts and percentage.

In addition, occurrences of Pradaxa® relevant ADRs will be analyzed relative to the number of patients treated as well as observed person-years (i.e. time at risk). If no concurrent Pradaxa® treatment is administered, then events occurring within a washout period of 3 days after discontinuation of Pradaxa® treatment will be assigned to the last treatment given. This washout period will also be included as time at risk for derivation of total person-years. ADRs that deteriorate under treatment will also be considered as “treatment emergent”. Events occurring prior to first intake of Pradaxa® treatment prescribed at baseline, during periods without Pradaxa® treatment (excluding washout periods), or after the end of the 6-month follow-up (excluding washout periods) will not be considered treatment emergent events, and will not be included in the summary tables.

Furthermore, serious adverse events will be listed with event narration. Adverse events will be coded using the latest version of Medical dictionary for regulatory activities (MedDRA) terminology.

The following parameters will be included in the safety analyses:

- Adverse drug reactions
- Adverse drug reactions leading to discontinuation of anticoagulation treatment
- Serious adverse drug reactions
- Adverse events leading to deaths

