11.2 ADVERSE EVENT AND SERIOUS ADVERSE EVENT COLLECTION AND REPORTING

The investigator shall maintain and keep detailed records of all AEs in their patient files.

Collection of AEs

The study design is of non-interventional nature and the study is conducted within the conditions of the approved marketing authorization. Sufficient data from controlled interventional trials are available to support the evidence on the safety and efficacy of the studied BI drug. For this reason, the following AE collection and reporting requirements have been defined.

The following must be collected by the investigator in the CRF from signing the informed consent onwards until the end of the study:

- All adverse drug reaction (ADRs) (serious and non-serious),
- All AEs with fatal outcome,

All ADRs, including those persisting after study completion must be followed up until they are resolved, have been sufficiently characterized, or no further information can be obtained.

The investigator should carefully assess whether an AE constitutes an ADR using the information below.

Causal relationship of adverse event

The definition of an adverse reaction implies at least a reasonable possibility of a causal relationship between a suspected medicinal product and an adverse event. An adverse reaction, in contrast to an adverse event, is characterized by the fact that a causal relationship between a medicinal product and an occurrence is suspected.

Medical judgment should be used to determine the relationship, considering all relevant factors, including the pattern of reaction, temporal relationship, de-challenge or re-challenge, and confounding factors such as concomitant medication, concomitant diseases, and relevant history.

Arguments that may suggest a **reasonable causal relationship** could be:

- The event is **consistent with the known pharmacology** of the drug
- The event is known to be caused by or **attributed to the drug class**.
- A **plausible time to onset of the event** relative to the time of drug exposure.
- Evidence that the **event is reproducible** when the drug is re-introduced
- **No medically sound alternative etiologies** that could explain the event (e.g. preexisting or concomitant diseases, or co-medications).
- The event is typically **drug-related and infrequent in the general population** not exposed to drugs (e.g. Stevens-Johnson syndrome).

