## 10.4 Safety Endpoints

- AEs (i.e. Pradaxa® relevant ADR (serious and non-serious), fatal AEs, and pregnancies)

Safety analyses will be performed separately for Cohort A and Cohort B.

The following parameters will be included in the safety analyses:

- Adverse drug reactions
- Adverse drug reactions leading to discontinuation of anticoagulation treatment
- Serious adverse drug reactions
- Adverse events leading to deaths

DRAFT

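### The treatment-emergent exclusion in SAP 11.5 is not limited to Pradaxa-relevant ADRs; read literally, it removes deaths off Pradaxa, including every death in a patient who stays on VKA, from the summary tables

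*SAP*

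**What the plan says.** Protocol 11.2 lists what the investigator must enter on the CRF from consent to the end of the study: all ADRs, and "All AEs with fatal outcome". No limit by drug or exposure is attached. Only the expedited-reporting table in the same section narrows fatal AEs to patients exposed to Pradaxa.

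SAP 10.4 defines the safety endpoint as "AEs (i.e. Pradaxa® relevant ADR (serious and non-serious), fatal AEs, and pregnancies", and names "Adverse events leading to deaths" as a parameter separate from the three ADR parameters. Safety is to be analysed separately for Cohort A and Cohort B. SAP 8.3 defines the Safety population as all enrolled patients with actual follow-up, so VKA initiators belong to it.

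The first paragraph of SAP 11.5 begins "Occurrences of Pradaxa® relevant ADRs will be analyzed relative to the number of patients treated" and goes on to person-years. It states that "events occurring within a washout period of 3 days after discontinuation of Pradaxa® treatment will be assigned to the last treatment given". It ends by naming events before first Pradaxa intake, "during periods without Pradaxa® treatment (excluding washout periods", or after the 6-month follow-up, and says that these "will not be considered treatment emergent events, and will not be included in the summary tables". A second paragraph plans AE incidence by System Organ Class and Preferred Term.

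Protocol 9.7.3 carries the same rule. It also says, in a preceding paragraph, that all adverse events will be summarised in frequency tables and, in a following one, that serious adverse events will be listed with narratives.

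**The concern.** For a VKA initiator who stays on VKA, the whole of follow-up is time without Pradaxa. A programmer who applies the exclusion as worded would take every death in that group out of the summary tables, along with any death in a Pradaxa patient whose fatal event began more than 3 days after stopping. The plan would then collect deaths in everyone, name them as a safety parameter, and summarise them only for time on Pradaxa.

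Death is the most serious outcome recorded here. A summary restricted in this way, read as though it covered the whole Safety population, would understate deaths on VKA and deaths after Pradaxa is stopped. The resulting distortion could make either treatment look better than it is.

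**Working it through.** The plan states no figure for this point, so the check is a comparison of texts followed by arithmetic on the planned sizes.

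**Comparison**

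| Element | Scope | Place |
|---|---|---|
| Collection of fatal AEs | All patients, consent to end of study | Protocol 11.2 |
| Expedited reporting of fatal AEs | Pradaxa-exposed patients only | Protocol 11.2 |
| Safety population | All enrolled with follow-up, VKA included | SAP 8.3 |
| Death parameter | Both cohorts, no causality or exposure condition | SAP 10.4 |
| Frequency tables | All adverse events | Protocol 9.7.3 |
| Exclusion from summary tables | Events outside Pradaxa exposure plus 3 days, or after 6 months | SAP 11.5, protocol 9.7.3 |

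The last row is incompatible with the Safety population, death-parameter and frequency-table rows unless it is confined to ADRs, and no sentence confines it. The expedited-reporting row shows that the authors wrote a Pradaxa restriction on fatal AEs where they wanted one.

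**Share of the Safety population affected**

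Inputs (SAP 7.4 and 7.1): Cohort A 300, Cohort B Pradaxa 500, Cohort B VKA 200, follow-up 6 months. Sum: 300 + 500 + 200 = 1000, which matches the stated total. The shares take all VKA initiators as remaining on VKA and all patients as followed throughout.

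- Share of all patients: 200 / 1000 = 20%.
- Share of Cohort B: 200 / (500 + 200) = 28.6%.
- Person-years at 6 months: 200 × 0.5 = 100 of 1000 × 0.5 = 500.
- Across the Visit 3 window: day 150 gives 200 × 150/365.25 = 82 of 411; day 210 gives 200 × 210/365.25 = 115 of 575. The share stays at 20%.

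**Time after stopping Pradaxa**

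The documents give no stopping rate. Assume that a fraction s of the 300 + 500 = 800 Pradaxa patients stop at mid follow-up and continue to be observed. Excluded person-years = 800 × s × (0.25 − 3/365.25) = 800 × s × 0.2418.

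| s (assumed) | Excluded person-years, Pradaxa patients | With the 100 VKA person-years, share of 500 |
|---|---|---|
| 5% | 9.7 | 21.9% |
| 10% | 19.3 | 23.9% |
| 20% | 38.7 | 27.7% |

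**Deaths**

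The documents give no mortality rate either. Purely as illustration, annual mortality of 1%, 3% or 5% over 100 VKA person-years gives 1, 3 or 5 deaths left out.

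**The case against.** The strongest reply is that the exclusion was meant only for the ADR analysis. Protocol 9.7.3 first deals with all reportable events. It then opens a new paragraph, introduced as an addition, on Pradaxa-relevant ADRs per patient and per person-year. The washout sentence in that paragraph already uses the word events while describing this rate calculation, and the exclusion closes the same paragraph. SAP 11.5 keeps the layout, with AE incidence in a separate paragraph. This reading is plausible and may well be what the authors intended. It shows that loss of deaths is not certain. It does not remove the conflict, because the closing sentence refers without limit to events and to the summary tables, and the SAP gives no separate rule for deaths.

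Second, excluded deaths would not vanish. A fatal event is serious by definition (protocol 11.1), so the protocol's SAE listing with narratives would show it, and SAP 12 says that no departure from the protocol is planned. That stands, but a listing does not correct an incomplete summary table, and SAP 11.5 does not repeat the listing.

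Third, a reader might infer that the death table will show zero deaths out of 200 for VKA. The documents do not support this. They specify safety analyses by cohort, state no split of Cohort B by treatment for safety, and the mock-up tables are not available. No VKA death row can be shown to be planned.

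Fourth, a reader might take the protocol 9.7.3 sentence "The assessment of safety will be based mainly on the frequency of adverse events, which includes" all serious adverse events as a false claim, because non-fatal SAEs judged unrelated are not collected on the CRF. That is too strong. The same paragraph has already defined AEs as the collected set, so the phrase can be read within that set, and SAP 11.5 does not carry it over. It is a minor wording point.

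Finally, follow-up after stopping is uncertain. Protocol 9.2.2, under its withdrawal criteria, treats a patient who does not complete 6 months of treatment as discontinued or withdrawn from treatment, and does not make clear how fully such patients are observed afterwards. The person-years in the stopping table are therefore conditional.

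**Conclusion.** The concern holds as a conflict between passages. The exclusion in SAP 11.5 and protocol 9.7.3, as worded, is wider than the analysis it sits in and contradicts the collection rule, the Safety population, the death parameter and the protocol's own statement that all adverse events will be summarised. It is not established that deaths will be missing from the final tables, since the narrower reading is open to whoever programs them.

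Under literal application, the part that needs no event or stopping rate is the VKA group: about 200 of 1000 planned patients and 100 of 500 person-years, assuming the planned allocation, continued VKA use and full follow-up. The further loss after Pradaxa is stopped depends on assumed stopping rates and on continued observation. The number of deaths affected cannot be derived from the documents, and the illustrative counts should not be quoted as estimates.

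This should be fixed, but it is not critical. The study's objectives are treatment perception and patient characteristics, safety is descriptive without hypothesis tests, and the primary and secondary PACT-Q endpoints are untouched.

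**What to change.** - In SAP 11.5 and protocol 9.7.3, state that the treatment-emergent exclusion applies only to Pradaxa-relevant ADR tables and person-year rates.
- Add one table of all fatal AEs from consent to end of study in the Safety population, by Cohort A, Cohort B Pradaxa and Cohort B VKA. Flag each death by onset: on Pradaxa, within 3 days of stopping, or off Pradaxa/on VKA.
- Carry the protocol's SAE listing with narratives into SAP 11.5.
- As a minor edit, align the protocol 9.7.3 reference to all serious adverse events with what the CRF collects, namely serious ADRs and fatal AEs.

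The cost is a few sentences and one extra table. Fatal AEs are already required on the CRF (protocol 11.2). Pradaxa start and end dates are collected if available (protocol 9.3.1), and discontinuation dates have their own CRF page (SAP 10.1). Where a date is missing, the onset flag should be shown as unknown. The SAP is still marked as a draft, so the change can be made before it is finalised.
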